All co-investigators have completed the CITI course and uploaded a copy of their certificates. All in-country data collectors will be trained by the PI in human subjects using the JHSPH guide.

4. If the PI will not personally be on-site throughout the data collection process, provide details about PI site visits, the supervision over consent and data collection, and the communication plan between the PI and study team.

The study manager and co-investigators involved in data management are Jhpiego employees and experienced in human subject research. Weekly telephone calls will take place during data collection.

B. Recordkeeping:

Describe how you plan to ensure that the study team follows the protocol and properly records and stores study data collection forms, IRB regulatory correspondence, and other study documentation. For assistance, contact [contact].

Protocol, IRB regulatory correspondence and other study documentation: We will establish a regulatory binder and keep it in the PI's office. A short binder of key forms will be shared with field co-investigators. We will develop and maintain a password protected study database for data management. Only de-identified data will be entered into the database. For logbooks that include identifiable data, these will be kept by the local study manager, under lock and key.

Study Data Collection Forms: Paper forms will remain in-country during data collection. They will be stored securely in the study team's possession or in a locked cabinet in each main Jhpiego country

office, under the supervision of a Monitoring and Evaluation Officer. Once entered into a database, and the data cleaned, paper forms will be destroyed.

C. Safety Monitoring

N/A

D. Reporting unanticipated problems/adverse events (AE's) to the IRB (***all studies must complete this section***):

Describe your plan for reporting to the IRB and (if applicable) to the sponsor. Include your plan for government-mandated reporting of abuse or illegal activity.

NOTE: The IRB does not require submission for all AEs, only those that are **unanticipated, pose risk of harm to participants or others, and are related to the study.**

Any adverse events will be reported to both the local and JHSPH IRBs in writing as soon as possible after the event occurs. Any loss of data will be reported using the IRB-mandated procedures. Any misinformation or incident related to the study, the data collection process or involving access to patient data will first be reported urgently to the PI who will gather as much information as possible, then report to IRB. The IRB support team at Jhpiego will be called upon to assist in such an eventuality.

E. Other IRBs/Ethics Review Boards:

If other IRBs will review the research, provide the name and contact information for each IRB/ethics review board and its Federal Wide Assurance, if it has one (available on OHRP's website at <http://www.hhs.gov/ohrp/assurances>).

The Oromia Regional Health Bureau IRB will review this study.

F. Collaborations with non-JHSPH Institutions:

For studies that involve collaboration with non-JHSPH institutions, complete the chart below by describing the collaboration and the roles and responsibilities of each partner, including the JHSPH investigator. This information helps us determine what IRB oversight is required for each party. Complete the chart for all multi-collaborator studies.

	Jhpiego	MOH (national and regional)	Arsi University
Primary Grant Recipient	X		
Collaborator		X	X

For the following, indicate "P" for "Primary", "S" for "Secondary" as appropriate to role and level of responsibility.) Add additional items if useful.

1	Human subjects research ethics training for data collectors	P	S	S
2	Day to day management and supervision of data collection	P	HEWs - S	S
3	Reporting unanticipated problems to the JHSPH IRB/Sponsor	P		S

4	Hiring/supervising people obtaining informed consent and/or collecting data	P	HEWs - S	S
5	Execution of plan for data security/protection of participant data confidentiality, as described in Sect. 5.	P		S

COMPLETE THE FOLLOWING SECTIONS WHEN RELEVANT TO YOUR STUDY:

XI. Secondary Data Analysis of Existing Data: see above

XIII. Creation of a biospecimen repository: N/A

XIV. Data Coordinating Center: N/A

XV. Drug Products, Vitamins, Food and Dietary Supplements: N/A

XVI. Investigational Medical Devices: N/A

Appendix 1. FP [and MNCH] Tasks by type of facility and cadre

Level of facility	Type of health personnel available	FP Services*	MNCH Services
Health Post	Health Extension Workers	
 • Counsel on FP and other RH issues • Counsel on natural FP methods • Provide injectables • Insert Implanon • Refer to health center for other long-acting and permanent methods • Do planning based on local data 	
 • Limited ANC + Referral to Health Center • PNC • Immunization
Health Center	Health Officers (HOs), Midwives, Clinical Nurses, Public Health Nurses, Laboratory Technicians	
The above activities, plus:
 
 • Conduct general physical and pelvic examinations, including VIA/VILI • Insert and remove implants • Insert and remove IUCD • (Where a trained GMP/HO is available), provide tubal ligation and vasectomy • Manage complications and side effects • Provide syndromic management of STIs • Provide HCT, including care • Train community-level workers and junior health professionals in FP • Conduct monitoring and facilitative supervision 	
The above activities, plus
 
 • Labor and delivery (BeMONC)
Primary Hospital	Non physician clinicians, GMPs, HOs, Midwives, Clinical Nurses, Public Health Nurses, Laboratory Technicians	
The above activities, plus:
 
 • Provide permanent methods of contraception • Receive referrals • Manage complications and side effects • Do work-ups for infertility 	
The above activities, plus:
 
 • Caesarean section • Blood transfusion • Receive Referrals • Manage Complications • KMC
General and Referral Hospitals	Obstetrician-Gynecologists, GMPs, HOs, Midwives, Clinical Nurses, Public Health Nurses, Laboratory Technicians	
The above activities, plus:
 
 • Manage infertility • Manage complicated STIs • Manage complications and side effects of contraceptive methods • Manage ROCs Perform research 	
The above activities, plus:
 
 • Emergency obstetric and newborn referral service

*Content on FP services taken verbatim from “National Guidelines for Family Planning Services in Ethiopia”, Federal Ministry of Health, 2011.

## Analysis Plan

### Utilizing All Health System Contacts to Offer Postpartum Family Planning (PPFP) to Pregnant Women and Women within Twelve Months Postpartum in Ethiopia

This plan describes how data collected through different methods will be analyzed after cleaning in order to meet these research objectives:

1. Estimate the added effect of the community-based intervention by comparing uptake of PPFP through 12 months postpartum in intervention and comparison sites (“intent to treat” analysis)
2. Assess the effect of systematically integrating PPFP messages into contacts with the health system on uptake of PPFP through 12 months postpartum using a dose-response analysis based on the number of contacts (“per protocol” analysis)
3. Explore the feasibility of tracking PPFP and reviewing data at health centers and HEWs and volunteers using record keeping and review processes to track women's decision-making and contraceptive use from pregnancy through 12 months postpartum
4. Explore factors influencing women's/couples' adoption of PPFP during the first 12 months postpartum

Quantitative and qualitative data analysis will be triangulated to help interpret results and provide deeper insights on study objectives.

#### A. Quantitative interviews with Women:

After data have been thoroughly examined for quality, the study team will perform exploratory data analysis of key variables such as checking frequency distributions, measures of variability, central tendency, and data outliers. We will also check for incomplete data and consider strategies to handle missing values such as undertaking an imputation strategy and weighting adjustments for non-responses.

We will compare differences by study arm for key variables. Analysis will account for clustering of variables at kebele (village) level using the Taylor linearization method. Differences between the arms for categorical variables will be assessed using the Pearson chi-squared test with the Rao-Scott correction. Differences in continuous variables will be assessed using an adjusted t-test. In case of substantial differences between the study arms, we will perform propensity score matching and perform the analysis with inverse probability weights.

Key descriptive variables:

- Sociodemographic data such as age, marital status, education, and socioeconomic status (nationally representative SES will be determined using the EquityTool described here: <http://www.equitytool.org/>)
- (Baseline only) Proportion of pregnant women with non-first pregnancies (non-primiparous) who previously used family planning
- Number of health system contacts where FP was discussed or provided, by type of contact (ANC, PNC, immunization, etc) and provider (facility provider, HEW, volunteer)
- Proportion of postpartum women who chose a method prior to delivery, by method, and received chosen method
- Proportion of postpartum women who used FP during the first 12 months after giving birth, by method
- Reasons for starting and stopping contraceptive methods and duration of use

- Initiation and duration of exclusive breastfeeding and lactational amenorrhea (LAM); average/median duration of postpartum amenorrhea, PP sexual initiation/PP abstinence
- Partner communication about family planning

We will fit multivariable logistic regression models for the primary and secondary binary outcomes (see below) to examine differences between the study arms, adjusted for confounding covariates and clustering at kebele level. We will also conduct a “per-protocol analysis” by examining the “dose-effect” of health system contacts on the primary and secondary outcomes, regardless of study arm. We will run two dose-effect models, looking at the association between the outcomes and 1) the total number of contacts and 2) the number of contacts during which FP was discussed as reported by the woman. For the secondary outcome, we will only include contacts during pregnancy since contacts after the birth would not have a temporal effect on whether the woman chose a method prior to delivery.

- Primary outcome:
  - Proportion of interviewed postpartum women who used a modern family planning method within 12 months after giving birth
- Secondary outcome:
  - Proportion of interviewed postpartum women who chose a method prior to delivery

We will also conduct time-to-event analyses using life-table method and use a log-rank test to test for differences in survival distributions between the study arms in terms of the timing of FP uptake after birth. We will perform multivariable hazards model (Cox’s proportional model or parametric model with Weibull distribution in case of non-normality in hazards function) for adjusting confounding covariates and clustering effects.

Additionally, we will run hazards regression models for women who initiated exclusive breastfeeding/LAM after birth to test for differences between arms in the duration of exclusive breastfeeding/LAM use.

- B. Key Informant interviews, Focus Group Discussions and In-Depth Interviews: In-depth interviews, focus group discussions, and key informant interviews will be translated and transcribed, then coded and analyzed using the MAXQDA software to facilitate data management. *A priori* codes will be developed for broad areas of interest for this study (perception of quality of interactions between women and providers, feasibility of incorporating PFP into community-based care, utility and feasibility of tracking tools, etc). Additional codes for themes and concepts that emerge within these broad categories will be developed using a Grounded Theory approach. Investigators will review transcripts together to develop a codebook. Investigators will then independently apply codes to several transcripts, compare results, discuss discrepancies, and make notes to enhance code definition and facilitate consistency in the coding process. Investigators will then code the remaining transcripts and analyze results for each theme.
- C. Supportive Supervision Forms: Data collected during supportive supervision visits to all study health centers and intervention health posts will be analyzed:
- Staffing changes, stock-outs and other service disruptions, completeness and use of data will be analyzed using descriptive statistics to assess fidelity to the intervention and implementation challenges
  - The quality of care will be analyzed by scoring checklists completed during observation of PFP counseling sessions and IUD/implant insertions to ascertain if there were improvements over time in the quality of services provided

- Client exit interview responses will be analyzed using descriptive statistics to assess the acceptability of the intervention from the perspective of end beneficiaries
- Provider interviews (conducted at first and last supervision visits) will be analyzed using descriptive statistics to identify fidelity to the intervention as reported by providers, implementation challenges, and acceptability of the intervention from the perspective of providers. Changes in provider knowledge between the first to last supervision visit will also be assessed.
- Information on stock-outs and quality of counseling will be used in the “per protocol” analyses.

In addition, service statistics were extracted from facility records during supervision visits and will be used to analyze FP uptake by method over the study period to triangulate with information reported by women.

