This study will be implemented 2 primary health care units (PHCUs), comprised of one health center and all kebeles/health posts in their catchment area, in Hitosa Woreda and 2 PHCUs in Lude-Hitosa Woreda. We randomly assigned 1 PHCU in each Woreda to the intervention and control arms. So out of 4 PHCUs in each Woreda, 1 was selected for intervention and 1 for control.

We obtained the total population for each PHCU. To estimate the number of women age 15-49 and expected pregnancies at the time of study survey, we used results from the Ethiopia mini DHS 2014: 43.6% of female residents of selected households were age 15-49 and 7.3% of women age 15-49 were currently pregnant at the time of the Mini DHS 2014.

Table 3: Estimation of eligible population

Arm	Total population	Female population (50%)	Expected females age 15-49 (43.6% of female pop)	Expected current pregnancies (7.3% of women 15-49)	Women 6-9 months pregnant (pregnancies / 3)
Intervention	72,138	36,069	15,726	1148	382
Comparison	52,508	26,254	11,446	835	278

For pregnant women, we calculated the minimum sample size requirements for this quasi-experimental design for the main outcome of interests (adoption of LAM and other modern method by 12-month PP) using the formula:

$$n' = \frac{\{z_{1-\alpha/2}\sqrt{2\bar{p}(1-\bar{p})} + z_{1-\beta}\sqrt{p_1(1-p_1) + p_2(1-p_2)}\}^2 (1 + (m-1)\rho)}{(p_1 - p_2)^2}$$

where, $p = (p_1 + p_2) / 2$

Where p_1 and p_2 are the proportions of women adopting LAM or other modern method in the intervention and control arms, respectively, and Z's are the critical value of the normal distribution at $\alpha=0.05$ and $\beta=0.20$; $1+(m-1)\rho$ captures the design-effect due to cluster based sampling of areas, where m = average size of the clusters and ρ =intra-cluster correlation. We consider a design-effect (deff) of 1.5 for adjusting higher intra-cluster correlation in the observations in the quasi-experimental design.

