We require a minimum of 299 women in postpartum observation period in each arm to detect an increase of at least 10% contraceptive prevalence rate (CPR) in the intervention arm, compared to the women in the control arm (20% vs 10% in the intervention and control arm, respectively) with $deff=1.5$ at 80% statistical power. Assuming about 20% lost-to-follow-up and non-response rate, we target to enroll 375 women in each arm. We consider that it will be sufficient to select 1 PHCU and its attached *kebeles* in each of the two *woredas* to ensure adequate sample size, with 2 PHCU randomly assigned to the intervention area (1 per *woreda*) and 2 to the control area (1 per *woreda*). The eligible women in 3rd trimester who consent to participate in the study voluntarily will be recruited and be interviewed at enrollment and at 12-month PP.

We used $p_1=0.2$ (20% PP contraceptive uptake by the final round of observation in the intervention arm) and $p_2=0.1$ (10% in the comparison arm). We considered $deff=(1+[m-1]\rho)= 1.5$. Because we are targeting 375 sample size of pregnant women in each arm consisting of 2 PHCUs, this implies $m=188$ AND $\rho=0.0027$.

Because the selected PHCUs are adjoining *woredas* of the same zone, it is expected that they will be quite similar, and in addition, the underlying population are all similar in terms of postpartum status; hence ρ very small (the larger the heterogeneity, the larger the ρ value). The Ethiopia DHS 2011 results suggest that the $deff$ of contraceptive use in all 11 regions are much smaller than the national level $deff$ of CPR (Appendix B – Estimates of Sampling Errors); *woreda* level $deff$ is expected to be much smaller due to less heterogeneity at *woreda* level, compared to the region/state level. In all regions, method specific $deff$ was <1.5 . So, we considered that of $deff=1.5$ is applied in this study is reasonable and practical. A study on postpartum use of contraceptive method at a *woreda* level in Ethiopia also had $deff=1.5$ (Abera Y, Mengesha ZB, Tessema GA. Postpartum contraceptive use in Gondar town, Northwest Ethiopia: a community based cross-sectional study. BMC Women's Health. 2015;15:19.)

Sample size requirements are included below based on the average number of providers and HDAs and managers in each *kebele*. See Table 4: Sample Size Summary

Table 4: Sample Size Summary

Study Participant	Intervention (2 PHCU)	Comparison (2 PHCU)	Total
Pregnant women	375	375	750

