Facility Providers working in ANC, L&D, postnatal care, immunization, family planning	10	10	40
District managers and stakeholders	Not applicable	Not applicable	6
Health Extension Workers (10 HPs in intervention clusters and 8 in comparison clusters; each HP has 2 HEWs)	20	16	36
HDA/HDA Team Leaders (2 FGD/PHCU, 10 people per FGD)	40	40	80
Total Sample Size	455	449	910

Since the expected number of eligible women in the selected control PHCUs is less than we require to meet this sample size, we will enroll women from adjoining kebeles (villages) in non-study PHCUs to reach the required sample size. The kebeles will be selected with local leadership and with the aim to minimize contamination by selecting villages further from the intervention PHCU. If we do not reach the required sample size in intervention PHCUs, we will also select adjoining kebeles to each the sample size minimum; the HEWs and HDA from these will be trained in the intervention package. All health centers in the entire woreda are receiving the same strengthening inputs, so no additional inputs will be necessary.

IV. Participants

Describe the study participants and the population from which they will be drawn. Specify the inclusion and exclusion criteria. If you plan to include children, note their ages and whether you will include children in foster care. Note if the participants are particularly vulnerable in terms of cognitive limitations, education, legal migration status, incarceration, poverty, or some combination of factors.

A. Inclusion criteria:

- Pregnant women (including emancipated minors)
- Providers (HDA, HEW, HCW, district managers providing PFP messages or services in study area)
- Willing to give informed consent

C. Exclusion criteria:

- Non – pregnant women, women living outside study area, facility providers not working in ANC, L&D, PNC or immunization. Providers from other points of service study facilities.

NOTE: If you are recruiting participants or receiving, accessing, or using data from a U.S. health care provider, HIPAA review is likely to be required. If you plan to bring identifiable health information from a foreign country to a U.S. covered entity (e.g., lab at the Hopkins SOM), HIPAA may be triggered. Check “yes” to the HIPAA question in the PHIRST application.

V. Study Procedures

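### The arms were formed by assigning four PHCUs, but the SAP clusters at kebele, so its p-values and intervals leave out most between-PHCU variance and the 80% power does not hold at PHCU level

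*SAP*

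**What the plan says.** Protocol section III.B gives the unit of assignment: "We randomly assigned 1 PHCU in each Woreda to the intervention and control arms". That makes four PHCUs, two per arm, in two woredas. The same section builds its design effect on that unit: "Because we are targeting 375 sample size of pregnant women in each arm consisting of 2 PHCUs", it takes m = 188 and an intra-cluster correlation (ICC) of 0.0027, which corresponds to the assumed design effect of 1.5. It argues that this ICC should be small because the PHCUs lie in adjoining woredas and "it is expected that they will be quite similar".

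SAP section A names a lower level. For the arm comparisons: "Analysis will account for clustering of variables at kebele (village) level using the Taylor linearization method". The primary and secondary logistic models are "adjusted for confounding covariates and clustering at kebele level". The hazards models are described as "for adjusting confounding covariates and clustering effects", with no level named. For timing of uptake the SAP will "use a log-rank test to test for differences in survival distributions between the study arms", and that sentence does not mention clustering.

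Neither document plans a PHCU-level analysis, a PHCU random effect or a small-sample correction to the degrees of freedom. Neither says that inference is conditional on the PHCUs selected. Protocol section III.B also allows control women to be added from kebeles of PHCUs outside the study, and the SAP does not say how those kebeles will be coded.

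**The concern.** The SAP's first objective is to estimate the added effect of the community intervention by comparing arms. Anything that makes one PHCU differ from another (access, staff performance, population) is shared by all of its kebeles and goes wholly into one arm. A variance built from differences between kebeles mostly misses this. A small p-value could therefore reflect which PHCUs were assigned to which arm, and the reader would have no sign of it. The sample size uses a normal critical value, which four assigned units do not support.

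**Working it through.** **1. The plan's own figures.** Inputs from Protocol section III.B: 20% versus 10%, two-sided alpha 0.05, power 80%, design effect 1.5. The stated formula gives 198.96 per arm before clustering; 198.96 × 1.5 = 298.4, rounded up to 299, as stated. Enrolment is 299/0.8 = 374 (stated 375). The ICC is 0.5/187 = 0.0027. All reproduce. The 0.0027 is back-calculated from the assumed design effect, so it is not an estimate.

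**2. Share of PHCU variance captured.** Table 4 counts health posts: "10 HPs in intervention clusters and 8 in comparison clusters". Assume one kebele per health post, equal sizes, and an even split between the two PHCUs of an arm. With K kebeles and PHCU variance σ², the true contribution to the variance of an arm mean is σ²/2. The expected contribution to the kebele-based estimate is σ²/[2(K−1)]. The share captured is 1/(K−1): 1/9 = 11% for K = 10 and 1/7 = 14% for K = 8.

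**3. Effect on the standard error at ICC 0.0027.** Take uptake of 15% in both arms and 300 women per arm, with kebele and woreda ICC 0.
- p(1−p) = 0.1275; sampling variance of the difference = 2 × 0.1275/300 = 0.00085.
- PHCU variance = 0.0027 × 0.1275 = 0.00034. Each arm contributes half, so the difference carries 0.00034.
- True variance = 0.00085 + 0.00034 = 0.00119.
- Kebele-based estimate = 0.00085 + 0.00017 × (1/9 + 1/7) = 0.00089.
- Ratio of standard errors = √(0.00089/0.00119) ≈ 0.87.

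Woreda variance works the other way. It cancels between arms, because each woreda has one PHCU in each, but the kebele variance still counts part of it. At an assumed woreda ICC of 0.02 it adds (0.02 × 0.1275/2) × (1/9 + 1/7) = 0.00032, so the estimate is 0.00122 and the ratio about 1.01.

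**4. Rejection rate under the null.** Simulation on the same layout (5+5 and 4+4 kebeles, t with 16 df, 40,000 runs per scenario, no covariates). Ranges are over the kebele and woreda ICCs shown. Only 0.0027 comes from the documents; every other ICC is an assumption.

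| PHCU ICC | Woreda ICC | Kebele ICC | Rejection at nominal 5% |
|---|---|---|---|
| 0 | 0 | 0–0.02 | about 5% |
| 0 | 0.01–0.02 | 0–0.02 | about 3–4% |
| 0.0027 | 0–0.02 | 0–0.02 | about 5.5–8.7% |
| 0.01 | 0–0.02 | 0–0.02 | about 10–17% |
| 0.02 | 0–0.02 | 0–0.02 | about 16–24% |

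**5. Power with the PHCU as the unit.** The difference is 0.10 with 299 women per arm.
- At design effect 1.5: SE = √(1.5 × (0.16 + 0.09)/299) = 0.0354. A normal critical value gives 81%. With t on 2 df (critical value 4.30) power is 36%; on 1 df, paired by woreda (12.71), it is 18%.
- At the followed-up cluster size, about 150 women per PHCU, the design effect is 1.40 and SE = 0.0342. Power is 37% and 18%. Interval half-widths are 4.30 × 0.0342 = 14.7 points and 12.71 × 0.0342 = 43.5 points.

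**6. Added control kebeles.** Table 3 expects 278 eligible women in the control PHCUs against a target of 375. The shortfall is 97, or 26% of the control arm.

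**The case against.** The protocol calls the design quasi-experimental and argues for a very small PHCU ICC. At the only value it gives, the inflation is modest. If there were no PHCU variance but some woreda variance, the kebele-clustered test would be conservative. The planned primary model adjusts for covariates, with propensity weighting if the arms differ substantially, so the simulated rates are not those of that model. Other parts of the plan bear on PHCU differences. Protocol objective 2a collects recalled earlier uptake, sections III.A and III.B equalise health-centre inputs, and SAP section C collects stock-outs, staffing changes and service statistics. All of this stands and belongs in the interpretation. None of it puts unmeasured PHCU variance into the standard error or adds degrees of freedom.

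Three stronger readings are tempting but unsupported.
- A reader might infer a false-positive rate of 17–24%. That needs PHCU ICCs that the documents do not give.
- A reader might infer that the log-rank test ignores clustering. The general clustering sentence in SAP section A may cover it, so the text is unclear but not shown to be wrong.
- A reader might infer that a PHCU-level test should replace the primary analysis. With 1 or 2 df it would be close to uninformative.

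**Conclusion.** The mismatch is real and undisclosed: PHCUs were assigned and used as the cluster for sample size, while the primary analysis clusters one level below. As written, the p-values and intervals do not separate the intervention from PHCU differences, and the 80% power does not apply at PHCU level. The error in the test's size is modest at ICC 0.0027. It could be absent or reversed with woreda variance, and larger if PHCUs differ more than the protocol assumes. The captured share and rejection rates rest on one kebele per health post, an even split between PHCUs, and no covariate adjustment. The PHCU-level power rests on the protocol's own rates and design effect, with no further kebele variance. The underlying limit is two PHCUs per arm, which no analysis removes. This should be fixed before the analysis. What is needed is disclosure and supporting results, not a new primary method.

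**What to change.** In the SAP:

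1. State that kebele-clustered intervals and p-values are conditional on the selected PHCUs and do not by themselves separate the intervention effect from PHCU differences.
2. Report uptake for each PHCU and the difference within each woreda, with recalled baseline uptake by PHCU beside them. Add a PHCU-level interval, with its degrees of freedom, as a supporting analysis. State that power at that level is about 36–37% (2 df, unpaired) or 18% (1 df, paired by woreda), not 80%.
3. Record the PHCU of every kebele, including control kebeles added from non-study PHCUs, and show the primary result with and without the added kebeles.

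As a minor clarification, name the clustering level for the hazards models and say whether the general clustering sentence covers the log-rank test.

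The cost is SAP wording, one PHCU code per kebele and a few tables, with no new data. The downside is a more modest claim and a supporting interval that is nearly uninformative.
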